2.8.4.2 Vital signs

Vital sign assessments are performed in order to characterize basic body function. The following parameters were collected: height (cm), weight (kg), body temperature ($^{\circ}$ C), heart rate (beats per minute), systolic and diastolic blood pressure (mmHg).

Data handling

Vital signs collected on treatment will be summarized. Values measured outside of on treatment period will be flagged in the listings.

Data analysis

For analysis of vital signs the clinically notable vital sign criteria are provided in [Table 2-5](#) below.

Table 2-5 Clinically notable changes in vital signs

Vital sign (unit)	Clinically notable criteria	
	above normal value	below normal value
Weight (kg)	increase > 10% from Baseline	decrease > 10% from Baseline
Systolic blood pressure (mmHg)	>=180 with increase from baseline of >=20	<=90 with decrease from baseline of >=20
Diastolic blood pressure (mmHg)	>=105 with increase from baseline of >=15	<=50 with decrease from baseline of >=15
Pulse rate (bpm)	>=100 with increase from baseline of >25%	<=50 with decrease from baseline of > 25%
Body temperature	>= 39.1	

The number and percentage of subjects with notable vital sign values (high/low) will be presented.

A listing of all vital sign assessments will be produced and notable values will be flagged. A separate listing of only the subjects with notable vital sign values may also be produced. In the listing, the assessments collected outside of on-treatment period will be flagged.

2.8.4.3 Ophthalmic Examination

The ophthalmic examinations of tonometry will be listed.

2.8.4.4 Echocardiograms (ECHO)

Descriptive statistics of the left ventricular ejection fraction (LVEF) change and percent change from baseline to worst post-baseline value will be provided.

2.8.4.5 ECOG performance status

The ECOG PS scale (Table 2-6) will be used to assess physical health of subjects, ranging from 0 (most active) to 5 (least active):

Table 2-4 ECOG Performance Scale

Score	Description
0	Fully active, able to carry on all pre-disease performance without restriction
1	Restricted in physically strenuous activity but ambulatory and able to carry out work of a light or sedentary nature, e.g., light house work, office work
2	Ambulatory and capable of all self-care but unable to carry out any work activities. Up and about more than 50% of waking hours
3	Capable of only limited self-care, confined to bed or chair more than 50% of waking hours

Score	Description
4	Completely disabled. Cannot carry on any self-care. Totally confined to bed or chair
5	Dead

Shift tables of ECOG performance status at baseline to worst post-baseline ECOG status by score will be provided. Shift tables of ECOG performance status at baseline to best post-baseline ECOG status by score will also be provided. ECOG performance status at each time point will be listed.

2.9 Pharmacokinetic endpoints

Not applicable for the final analysis as PK has already been analyzed and reported in the previous CSR, and no new PK data was collected since the primary analysis.

2.10 PD and PK/PD analyses

Not applicable.

2.11 Patient-reported outcomes

Not applicable.

2.12 Biomarkers

Not applicable.

2.14 Interim analysis

There is no interim analysis planned for this study.

3 Sample size calculation

3.1 Primary analysis

Approximately 65 subjects will be enrolled primarily based on clinical justification. This sample size was deemed to be sufficient to assess efficacy, safety and tolerability of Dabrafenib in combination with trametinib in Asian subjects with BRAF V600 Mutation-Positive Melanoma.

An exact binomial confidence interval will be calculated. Lower bound higher than 25% is considered to be clinically meaningful in this setting.

3.2 Power for analysis of key secondary variables

Not applicable.

4 Change to protocol specified analyses

Replace All Treated Subjects (ATS) to Full Analysis Set (FAS).

Mainland Chinese patients data from 01-Jul-2019 onwards are not included due to local regulations in China (lack of HGRAC approval).

5 Appendix

5.1 Imputation rules

In general imputed partial dates will not be used to derive study day, duration (e.g. duration of adverse events), or relapse time variables. In addition, imputed dates are not used for deriving the last contact date in overall survival analysis dataset.

5.1.1 Study drug

The following rule should be used for the imputation of the dose end date for a given study treatment component:

Scenario 1: If the dose end date is completely missing and there is no EOT page and no death date, the subject is considered as on-going:

The subject should be treated as on-going and the cut-off date should be used as the dose end date.

Scenario 2: If the dose end date is completely or partially missing and the EOT page is available:

Case 1: The dose end date is completely missing, and the EOT completion date is complete, then this latter date should be used.

Case 2: Only Year(yyyy) of the dose end date is available and yyyy < the year of EOT date:

Use Dec31yyyy

Case 3: Only Year(yyyy) of the dose end date is available and yyyy = the year of EOT date:

Use EOT date

Case 4: Both Year(yyyy) and Month (mm) are available for dose end date, and yyyy = the year of EOT date and mm < the month of EOT date:

Use last day of the Month (mm)

Case 5: Both Year(yyyy) and Month (mm) are available for dose end date, and yyyy = the year of EOT date and mm = the month of EOT date:

Use EOT date

For subject with missing exposure end dates at the time of data cutoff, the exposure end date will be imputed to the earliest of: the date of the data cutoff, the date of withdrawal from the study, or the death date.

The imputed exposure end date will be used to calculate cumulative dose and exposure duration. The imputed exposure end date will be stored in the exposure analysis dataset and an exposure end date imputation flag variable will be derived indicating which exposure end date records are imputed. Imputed exposure end dates will also be stored on the study treatment end date variable.

For subjects who have missing end dates in their last exposure record because they are still on study treatment, the on-therapy indicator variables (time in relation to study treatment) are assigned to on-therapy for all records where the 'dataset'.date' is after or on the study treatment start date. Missing exposure end date imputation will be applied to both study treatments (dabrafenib and trametinib). The study treatment end date variable will hold the last date of exposure across both study treatments.

All other cases should be considered as a data issue and the statistician should contact the data manager of the study.

After imputation, compare the imputed date with start date of treatment, if the imputed date is < start date of treatment:

Use the treatment start date

Subjects with missing start dates are to be considered missing for all study treatment component related calculations

5.1.2 AE, ConMeds and safety assessment date imputation

Table 5-1 Imputation of start dates (AE, CM) and assessments (LB, EG, VS)

Missing Element	Rule
day, month, and year	
 No imputation will be done for completely missing dates
day, month	
 If available year = year of study treatment start date then 
 If stop date contains a full date and stop date is earlier than study treatment start date then set start date = 01JanYYYY Else set start date = study treatment start date. If available year > year of study treatment start date then 01JanYYYY If available year < year of study treatment start date then 01JulYYYY
Day	
 If available month and year = month and year of study treatment start date then 
 If stop date contains a full date and stop date is earlier than study treatment start date then set start date = 01MONYYYYY. Else set start date = study treatment start date. If available month and year > month and year of study treatment start date then 01MONYYYYY If available month and year < month year of study treatment start date then 15MONYYYYY

Table 5-2 Imputation of end dates (AE, CM)

Missing Element	Rule (* = last treatment date plus 30 days provided it is not > (death date, cut-off date, withdrawal of consent date))
day, month, and year	
 Completely missing end dates (incl. ongoing events) will be imputed by the end date of the on-treatment period* For post treatment period, no imputation will be done for completely missing dates
day, month	
 If partial end date contains year only, set end date = earliest of 31DecYYYY or end date of the on-treatment period *

Missing Element	Rule (* = last treatment date plus 30 days provided it is not > (death date, cut-off date, withdrawal of consent date))
	
 For post treatment period, set end date = earliest of 31DecYYYY or death date or cut-off date or withdrawal of consent date
Day	
 If partial end date contains month and year, set end date = earliest of last day of the month or end date of the on-treatment period* For post treatment period, set end date = earliest of last day of the month or death date or cut-off date or withdrawal of consent date
Date of progression from Prior anti-cancer therapy	
 Only impute when a month and year are available but the day is missing. Impute to last day of the month, also must be after the start date of therapy and prior to 'start of study treatment'. If 'start of study treatment' is on the same month as prior therapy end date, then assign treatment start date minus one day for the prior therapy end date. 

Any AEs and ConMeds with partial/missing dates will be displayed as such in the data listings.

Any AEs and ConMeds which are continuing as per data cut-off will be shown as 'ongoing' rather than the end date provided.

5.1.3 Other imputations

Incomplete date of initial diagnosis of cancer and date of most recent recurrence

Missing day is defaulted to the 15th of the month and missing month and day is defaulted to 01-Jan.

Incomplete assessment dates for tumor assessment

All investigation dates (e.g. MRI scan, CT scan) must be completed with day, month and year. If one or more assessment dates are incomplete but other investigation dates are available, this/these incomplete date(s) are not considered for calculation of the assessment date and assessment date is calculated as the latest of all investigation dates (e.g. MRI scan, CT scan) if the overall response at that assessment is CR/PR/SD/UNK. Otherwise – if overall response is progression – the assessment date is calculated as the earliest date of all investigation dates at that evaluation number. If all measurement dates have no day recorded, the 1st of the month is used. If the month is not completed, for any of the investigations, the respective assessment will be considered to be at the date which is exactly between previous and following assessment. If a previous and following assessment is not available, this assessment will not be used for any calculation.

Applying the cut-off to tumor assessment

For tumor related assessments, if an evaluation has some assessments done prior to cut-off date and others after the cut-off date, then the evaluation is considered post-cut-off date and will be excluded from analysis.

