Refer to the Time and Events Table ([Table 20](#)) for the timing of all assessments. Assessments must be performed on a calendar schedule; delays in treatment administration will not delay performance of assessments. Details on efficacy and safety assessments are presented in [Section 7.2](#) and [Section 7.3](#), respectively. [REDACTED]

[REDACTED] Further details of study procedures and assessments can be found in the SPM.

[figure not shown]
Investigators may be requested to perform additional safety tests during the course of the study based on newly available data to ensure appropriate safety monitoring. Appropriate local regulatory and ethical approvals should be obtained before any additional testing is performed.

[Table 20](#) outlines study assessments and their timing.

Table 20 Time and Events Table

STUDY PHASES ¹	SCREENING ²	TREATMENT					FOLLOW-UP		
		Day 1	Day 15	Every 4 Weeks	Every 8 Weeks	Every 12 Weeks	Treatment Discontinuation ²⁷	Contact	Conclusion
Visit Window (Days)	(≤ 28 except where noted) ²		(± 3)	(± 3)	(± 7)	(± 7)	(± 7)	(± 7)	N/A
CLINICAL ASSESSMENTS¹									
Informed consent ³	X								
Demographic data	X								
Past and current medical conditions including cardiovascular medical history and risk factors	X	X ⁴							
Family history (cardiac, cancer)	X								
Disease characteristics ⁵	X								
Prior anti-cancer therapies	X								
Tumor tissue for BRAF V600 mutation testing (required for eligibility) ⁶	X								
Brain MRI/CT ⁷	X				X ⁷				
Lesion assessment ⁸	X	Week 8, and every 8 weeks through Week 56, then every 12 weeks thereafter (all ± 7 days) until disease progression							
Performance status (ECOG)	X	X ⁴		X			X		
Enrollment		X							
SAFETY ASSESSMENTS¹									
Physical examination ⁹	X (Complete)	X ⁴		X (Brief)			X (Complete)		
Dermatological examination (including skin lesion photography) ¹⁰	X				X		X		
Ophthalmic examination ¹¹	X			X Only at week 4					
Vital signs ¹²	X			X			X		
Adverse events ¹³	X	X		X			X	X	X
Concomitant medications ¹⁴	X	X		X			X	X	

STUDY PHASES ¹	SCREENING ²	TREATMENT					FOLLOW-UP		
		Day 1	Day 15	Every 4 Weeks	Every 8 Weeks	Every 12 Weeks	Treatment Discontinuation ²⁷	Contact	Conclusion
Visit Window (Days)	(≤ 28 except where noted) ²		(± 3)	(± 3)	(± 7)	(± 7)	(± 7)	(± 7)	N/A
ECG ¹⁵	X (5 weeks)		X	X (only at Week 4, 8 and 12)		X (after week 12)	X		
ECHO ¹⁶	X (5 weeks)			X (only at Week 4)		X			

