5.4 Statistical models

5.4.1 Primary endpoint analysis

Overall response rate

Responses will be summarized in terms of percentage rates with 95% CIs. An exact binomial confidence interval (implemented using SAS procedure FREQ with EXACT statement) will be calculated [Clopper and Pearson 1934]

SAS procedure FREQ will be used to estimate the proportion of responders (binary outcome = 1 or “Yes”), along with the associated 95% ($=100 \times (1 - \text{two-sided } \alpha \text{ level})$) two-sided Pearson-Clopper CI.

Overall response will be determined using only target, non-target, and new lesions, using the criteria specified in the protocol.

Table 5-3 Evaluation of Overall Response for Subjects

Target Lesions	Non-Target Lesions	New Lesions	Overall Response
CR	CR or NA	No	CR
CR	Non-CR/Non-PD or NE	No	PR
PR	Non-PD or NA or NE	No	PR
SD	Non-PD or NA or NE	No	SD
NE	Non-PD or NA or NE	No	NE
PD	Any	Yes or No	PD
Any	PD	Yes or No	PD
Any	Any	Yes	PD

CR=complete response, PR = partial response, SD=stable disease, PD=progressive disease, NA= Not applicable, and NE=Not Evaluable

Evaluation of Best Overall Response

The best overall response is the best response recorded from the start of the treatment until disease progression, death, or withdrawal of consent, whichever occurs first. Best overall response will be determined programmatically based on the investigator’s assessment of response at each time point.

- To be assigned a status of SD, follow-up disease assessment must have met the SD criteria at least once after enrollment for a minimum of 49 days.
- If the minimum time for SD is not met, best response will depend on the subsequent assessments. For example, if an assessment of PD follows the assessment of SD and SD does not meet the minimum time requirement, the best response will be PD. Alternatively, subjects lost to follow-up after an SD assessment not meeting the minimum time criteria will be considered NE.

Confirmation Criteria:

- To be assigned a status of PR or CR, a confirmatory disease assessment should be performed no less than 4 weeks (28 days) after the criteria for response are first met.
- Confirmed best overall response will be determined programmatically based on RECIST 1.1.

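### SAP 5.1.3 drops a final progression evaluation that has no usable month, so a documented PFS or DOR event becomes censoring or a later death

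*SAP*

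**What the plan says.** SAP 5.1.3, under incomplete tumour assessment dates, sets out a sequence:

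- The requirement: "All investigation dates (e.g. MRI scan, CT scan) must be completed with day, month and year."
- Some dates incomplete, others available: "If one or more assessment dates are incomplete but other investigation dates are available, this/these incomplete date(s) are not considered". The evaluation then takes the latest available date, or the earliest if the response is progression.
- Day missing throughout: "If all measurement dates have no day recorded, the 1st of the month is used."
- Month missing: "If the month is not completed, for any of the investigations, the respective assessment will be considered to be at the date" halfway between the assessments on either side.
- No such neighbours: "If a previous and following assessment is not available, this assessment will not be used for any calculation."

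The last two rules make no exception for progression. They use neither the recorded year nor the scheduled visit.

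Three other places decide what follows. Protocol Table 20 schedules lesion assessment at "Week 8, and every 8 weeks through Week 56, then every 12 weeks thereafter (all ± 7 days) until disease progression". Its footnote 8 and Protocol 4.2.2 continue scanning for subjects who stay on treatment after progression. SAP 2.7.1 does not accept discontinuation for progression as a PFS event without objective RECIST evidence. SAP 2.7.3 censors at the last adequate assessment when there is no event, when new anti-cancer therapy comes first, or when a death or PD follows two or more missed assessments. DOR uses the same censoring rules.

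**The concern.** A midpoint needs an assessment on each side, and a final scan has none after it. Outside treatment beyond progression, the PD scan is the final scan. The same clerical gap is therefore harmless for an SD or PR in mid-series and removes a PD altogether. Whether an evaluation is kept depends on its outcome, which makes the resulting censoring informative.

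The trial has one arm, so no control group shares the bias. PFS and DOR will be read as absolute medians, and a rule that removes events flatters both. A final confirming CR or PR scan can also be dropped. That would turn a confirmed responder into a non-responder in the final ORR, at 1/65 = 1.5 percentage points each.

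**Working it through.** **1. Trace the rule by type of evaluation.** The plan gives no figure to reproduce here, so the first check is textual.

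| Evaluation with a missing month | Treatment under SAP 5.1.3 | Effect on PFS/DOR |
|---|---|---|
| SD or PR in mid-series, no usable month | Kept, dated at the midpoint | None of note |
| PD, another investigation dated | Dated from that investigation (second sentence) | Event kept |
| PD, no usable month, scans continue after progression | Kept, dated at the midpoint | Event kept, date approximate |
| PD, no usable month, last scan | Dropped | Event censored or delayed |
| SD or PR, no usable month, last scan | Dropped | Censoring moves back one scan |

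**2. Check the windows within which a later death still counts (SAP 2.7.3).** They agree with the scan schedule:

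- day limits: 56×7+7 = 399 and 80×7+7 = 567
- look-back: 16×7+7 = 119, (8+12)×7+7 = 147 and 24×7+7 = 175 days

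**3. Work one subject through.** The last adequate scan is at Week 16 (16×7+1 = day 113). The PD scan is at Week 24 (nominal day 24×7+1 = 169), has no month on any investigation, and is the last scan. It is dropped, and PFS is censored at day 113. A later death is an event only up to day 113+119 = 232, which is 63 days after the nominal PD date, and only if no new therapy was started. The same reasoning gives 63 days for a Week 68 PD after a Week 56 scan (393+147 = 540; 540−477 = 63). It gives 91 days for a Week 92 PD after a Week 80 scan (561+175 = 736; 736−645 = 91).

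**4. Illustrate the size.** The documents give no rate of missing months, so the rates are assumed. Other inputs: 65 subjects (Protocol 4.1.1); the Table 20 schedule; exponential progression times with median 9.3 or 11.4 months, the two phase III medians for the combination in Protocol 1.2.3; follow-up uniform over 12 to 36 months; 1,000 simulated trials per row. Every affected PD scan is taken as terminal, with no rescue by death, so each row shows the most that rate would do.

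| PD scans dropped | Events (9.3) | KM median, months (9.3) | Shift | Events (11.4) | KM median, months (11.4) | Shift |
|---|---|---|---|---|---|---|
| 0% | 51.5 | 10.26 | – | 47.1 | 12.68 | – |
| 2% | 50.4 | 10.51 | 0.25 | 46.3 | 12.79 | 0.11 |
| 5% | 48.9 | 10.73 | 0.47 | 44.9 | 13.07 | 0.39 |
| 10% | 46.2 | 11.40 | 1.14 | 42.5 | 13.95 | 1.27 |
| 20% | 41.0 | 12.78 | 2.52 | 37.5 | 15.78 | 3.10 |

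The 0% medians exceed 9.3 and 11.4 because progression is dated at the scan that detects it. Rows are separate runs, so the shifts carry some simulation error, which matters most at 2%.

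**The case against.** **Such evaluations should be rare.** Complete dates are required, Protocol Section 8 commits to resolving data errors, and scans are stored, so a missing month can be queried. This stands, and it limits the size. Nothing in the documents supports 2% or 10% as an expected rate. At 2% the shift is 0.11 to 0.25 months, or 3 to 8 days at 30.4375 days per month, about the ±7-day scan window.

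**Final SD and PR scans are dropped too.** True, but the effects are not equal. With d events among n at risk at a scan, deleting a PD changes d/n to (d−1)/(n−1), a fall of (n−d)/[n(n−1)]. Deleting a final SD changes it to d/(n−1), a rise of d/[n(n−1)]. Scan for scan, the lost PD weighs more whenever fewer than half of those at risk progress at that scan.

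**A reader might infer that one undated photograph discards a fully dated CT.** The missing-month sentence can be read that way, because *any* may mean at least one investigation. The sentence on available dates comes first, though, and would date that evaluation from the CT. Read in order, the rule applies when no investigation has a usable month. This is an ambiguity to remove, not a clear contradiction.

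**A reader might infer that the event is always lost.** It is not: subjects scanned beyond progression keep their PD, and an in-window death without new therapy still counts.

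**A reader might infer that the first-of-month rule threatens ORR.** If only the confirming scan lacks its day D, the computed gap is the true gap minus (D−1). At the 8-week interval, 56−(D−1) falls below 28 only when D is 30 or 31, which is 18 of 365 days, about 5%. Shorter gaps are more exposed, but Protocol 7.2.2 still requires the next scheduled evaluation after an early confirmation. Another fixed day would only be another convention. I do not pursue this.

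**The primary ORR analysis is already done.** It used a cut-off of 23-Feb-2018 under a previous SAP. Only the final ORR could be affected, and only where the confirming scan is the subject's last.

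**Conclusion.** The point holds in a limited form. A terminal PD evaluation with no usable month on any investigation is excluded from every calculation, and the subject is censored at the last adequate assessment unless an in-window death supplies a later event. Losing a progression this way can only lengthen PFS and DOR. The direction follows from the text alone. The size rests on a count the documents do not give: close to nothing if no such evaluation exists, about 0.1 to 0.3 months on median PFS at an assumed 2%, and 1.1 to 1.3 months at an assumed 10%, under the assumptions shown. Because complete dates are mandated, the low end is the more plausible. PFS and DOR are descriptive secondary endpoints, so no test is at risk. The case for change is that the deletion depends on outcome and is cheap to remove.

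**What to change.** In SAP 5.1.3:

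(a) In the missing-month sentence, change *any* to *all*, so that an evaluation with at least one usable date is dated from it, in line with the sentence on available dates.

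(b) Replace the last sentence for two cases, leaving other terminal evaluations as they are:

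- *A PD evaluation with no usable month and no following assessment is retained as an event. It is dated at its scheduled visit, bounded by the recorded year, the previous assessment, and the earliest of new anti-cancer therapy, death and the applicable cut-off. It is excluded only if it cannot be placed on or before that cut-off.*
- *A confirming CR or PR with no usable month counts only if the visit sequence shows at least 28 days since the first response.*

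The exclusion is needed because SAP 2.1.1 bars mainland Chinese data from 01-Jul-2019 onwards, and a bounded date must not bring a later scan inside that limit. The condition on confirmation is needed because SAP 5.4.1 says that "a confirmatory disease assessment should be performed no less than 4 weeks (28 days) after the criteria for response are first met", so the interval has to be shown and not assumed.

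(c) Report the number of evaluations affected, by response category.

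The cost is SAP wording and a few lines of derivation code. The downside is that a few event dates become approximate. SAP 5.1.1 and 5.1.2 already accept this for dose and adverse event dates, which are imputed from the recorded year, end of treatment, death or cut-off.
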